11 SAFETY ANALYSES

11.1 ADVERSE EVENTS

An AE (classified by preferred term) occurring after the first dose of study medication and up to the last dose of study medication +28 days is considered a treatment emergent adverse event (TEAE) if it was not present prior to the first dose of study medication, or it was present prior to the first dose of study medication but increased in severity during the treatment period.

The number and percentage of subjects reporting TEAEs are tabulated by system organ class and preferred term. If more than one event occurs with the same preferred term for the same patient, the patient is counted only once for that preferred term using the most severe and most relatedness occurrence for the summarization by severity and by relationship to the study medication. In addition to the frequency tables above, crude event rate are provided. The crude event rate of interest (per 100 patient exposure years) by system organ class and preferred term is calculated as: number of the events per PT and SOC / total patient exposure years (PEY)*100.

The following TEAE table and listings are provided.

1. TEAE by system organ class and preferred term
2. TEAE by system organ class, preferred term, and maximum severity
3. TEAE by system organ class, preferred term, and relationship to study medication
4. Treatment-emergent serious AEs (TESAE) by system organ class and preferred term
5. TEAEs leading to discontinuation of study medication or from the study will be summarized by preferred term and treatment group
6. Listing of subjects with serious adverse events (SAEs)
7. Listing of subjects with adverse events leading to discontinuation of study medication or from the study

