7.1.1.1.6. Termination / Early Termination (ET) Visit

This visit is to occur 4 weeks after final dose. If a subject discontinues from the study during the treatment period, perform the ET assessments at the time of withdrawal from dosing:

- Physical examination
- Weight (use dry weight in HD subjects)
- Vital signs: BP, HR, and respiratory rate
- 12-lead ECG
- Laboratory tests:
 - CBC with WBC differential and reticulocyte count
 - Fasting serum chemistry (with LFTs, lipid profile, and glucose)
 - hCG test for women of childbearing potential only
 - Serum iron studies: iron, ferritin, transferrin (or TIBC), and TSAT
 - Special labs (CHr, hepcidin, hs-CRP, plus select biomarkers) (only for subjects who had a baseline collected during prior roxadustat study)
- Quality of Life questionnaire (FACT-An)
- Adverse events
- Concomitant medications

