7.2. Post-Treatment Follow-Up Period

The Follow-up Period begins on the week after the last dose of study treatment, and continues for 4 weeks.

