11.3. Procedures for Eliciting, Recording, and Reporting Adverse Events

11.3.1. Adverse Event Reporting Period

The study period during which all AEs and SAEs must be reported begins after informed consent is obtained and ends 28 days after the last treatment.

Adverse events will be followed until resolved, stable, or until the subject's last study visit. If an AE is not resolved or stabilized at the subject's last visit, it is up to the discretion of the investigator and study medical monitor to determine if further monitoring of the event is warranted.

Adverse events collected prior to dosing of study drug will be considered "treatment non-emergent" while those reported after the first dose of study drug will be considered "treatment emergent" and be assessed for relationship to study drug.

During the AE reporting period, study site personnel will query each subject at each visit to actively solicit any AE occurring since the previous visit. This does not preclude the site from collecting and recording any AEs reported by the subject to site personnel at any other time.

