8 STUDY MEDICATION

8.1 EXTENT OF EXPOSURE AND DOSE ADMINISTRATION

Treatment duration, the Patient-Exposure-Year (PEY) are defined as (Last Dose Date – First Dose Date + 1)/365.25, during this study.

Average weekly study dose (in mg or mg/kg) are summarized for selected time periods such as every 4 weeks, from week 0 – 24, every 8 weeks, from week 25-48, and every 12 weeks, starting week 49 through EOT/ET.

Dose adjustment frequencies (number (%)) of subjects with a dose increase, dose decrease, dose hold, separately)

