10.1 ANALYSES OF EFFICACY ENDPOINTS

The following efficacy endpoints based on the observed data will be summarized at the analysis visits in Section 13.1:

- Mean Hb values over selected time ; mean Hb overlay mean weekly roxadustate dose over time plot.
- Number (%) of subjects with mean Hb at ≥ 10 g/dL averaged over selected time periods
- Number of rescue therapy events (composite of transfusions, IV iron, ESAs) of total PEY (defined as the sum of all subject's individual PEY) and number of individual rescue therapy modalities of total PEY (this can be expressed as per 100 PEY dependent on the magnitude of the result). PEY is defined as $(\text{last dose date} - \text{first dose date} + 1) / 365.25$
- Mean monthly oral iron dose (note the monthly dose is defined as sum of weekly dose over 4 weeks) at specific time periods
- Mean Reticulocyte hemoglobin content (CHr) at selected time points
- Mean Highly sensitive C-reactive protein (hs-CRP) at selected time points
- Mean Hepcidin levels in serum at selected time points
- Mean eGFR at selected time points
- Mean Total Cholesterol, LDL cholesterol, LDL/HDL ratio, HDL cholesterol, non-HDL cholesterol at selected time points

- Mean TSAT and Ferritin at selected time points

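### Crude TEAE rates count events to 28 days after last dose but divide by exposure ending at last dose, so every non-zero rate runs slightly high

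*SAP*

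**What the plan says.** **Numerator.** SAP 11.1 starts the TEAE window after the first dose. An event "up to the last dose of study medication +28 days is considered a treatment emergent adverse event", provided it is new or has worsened in severity.

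**Rate.** The same section adds a crude event rate per 100 patient-exposure-years by system organ class and preferred term: "number of the events per PT and SOC / total patient exposure years (PEY)*100".

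**Denominator.** SAP 8.1 gives "Treatment duration, the Patient-Exposure-Year (PEY) are defined as (Last Dose Date – First Dose Date + 1)/365.25, during this study". SAP 10.1 repeats that formula for the rescue-therapy rates and sums it over subjects: "of total PEY (defined as the sum of all subject's individual PEY". Neither document defines another time at risk for adverse events.

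**Collection.** Protocol 11.3.1 states that the reporting period "begins after informed consent is obtained and ends 28 days after the last treatment", and Protocol 7.2 provides a matching follow-up: "The Follow-up Period begins on the week after the last dose of study treatment, and continues for 4 weeks". Events in the 28 days after last dose are therefore collected and can enter the numerator.

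**The concern.** A rate per unit of time needs events and time taken from the same window. Here the event window is longer than the time window by up to 28 days per subject, always in the same direction.

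Long-term safety is part of the primary objective (Protocol 2.1, SAP 2), and the crude rate is the only adverse-event summary in SAP 11.1 that allows for length of exposure. There is no control group (Protocol 4.1.1), so these rates will be read as absolute figures or set beside rates from other studies. If another study matches its windows, such a comparison carries a small artefact of definition.

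**Working it through.** The plan states no event count, rate or mean exposure, so there is no figure of its own to reproduce. The check is direct arithmetic.

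**Inputs**
- Subjects: 15 (SAP 3).
- Event window: after first dose to last dose + 28 days (SAP 11.1).
- Time per subject: T = (last dose - first dose + 1)/365.25 (SAP 8.1, 10.1).
- Post-dose observation per subject: f, at most 28/365.25 = 0.0767 years.
- Mean treatment time: not given, so assumed. The planned maximum is 312 weeks (SAP 3).

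**Formulas**, with E the number of events for a given term:
- SAP rate = 100 x E / sum(T)
- Matched-window rate = 100 x E / sum(T + f)
- Ratio of the two = 1 + sum(f)/sum(T)

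E cancels. The ratio is therefore the same for every preferred term and system organ class with at least one event, and does not depend on when in the window the events fell. A rate of zero stays zero.

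**Maximum time omitted:** 15 x 28/365.25 = 1.15 patient-years, if all 15 subjects are observed for the full 28 days.

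**Upper-bound overstatement by assumed mean treatment time**, illustrated with 10 events:

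| Assumed mean | Total PEY | Matched time | Overstatement | SAP rate | Matched rate (per 100 years) |
|---|---|---|---|---|---|
| 52 weeks (about 1 year) | 14.95 | 16.10 | 7.7% | 66.9 | 62.1 |
| 104 weeks (about 2 years) | 29.90 | 31.05 | 3.8% | 33.5 | 32.2 |
| 156 weeks (about 3 years) | 44.85 | 46.00 | 2.6% | 22.3 | 21.7 |
| 260 weeks (about 5 years) | 74.74 | 75.89 | 1.5% | 13.4 | 13.2 |
| 312 weeks (about 6 years) | 89.69 | 90.84 | 1.3% | 11.15 | 11.01 |

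Example row: 15 x 260 x 7/365.25 = 74.74; 74.74 + 1.15 = 75.89; 75.89/74.74 = 1.015.

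**Incomplete follow-up.** If only half the post-dose time is observed, the excess halves: 0.5 x 28/364 = 3.8% at 52 weeks and 0.5 x 28/1820 = 0.8% at 260 weeks.

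**Cutting the numerator at last dose instead.** At 260 weeks, if 1 of 10 events is post-dose, the rate becomes 100 x 9/74.74 = 12.0 rather than 13.4. If none is post-dose, it stays at 13.4. This is the on-drug rate, a different quantity from the matched-window rate.

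**Scale of random error.** For 10 events over 74.74 PEY, the exact Poisson 95% interval is about 6.4 to 24.6 per 100 years, against a shift from 13.4 to 13.2.

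**The case against.** The strongest reply is that this hardly matters. The SAP calls the rate crude and prints both definitions. The protocol's own adverse-event summary (10.6.4) is the number and percentage of subjects with TEAEs, which the mismatch does not touch. The study is single-arm, descriptive and has 15 subjects, so the shift is far inside random error. The direction overstates harm, so it cannot hide a signal.

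The omitted time may also be less than the maximum. For subjects who discontinue early, the protocol says to "perform the ET assessments at the time of withdrawal from dosing" (7.1.1.1.6), and withdrawn subjects are advised, not obliged, to complete the 4-week follow-up (Section 8). A death on treatment or soon after adds little or no post-dose time.

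All of this stands as a limit on size and consequence. It does not remove the mismatch: no text says that the two windows differ or why, and a table showing only the rate would not reveal it.

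A reader might infer that a cluster of events just after stopping makes the error larger. The documents do not support that. They give no information on event rates after last dose, and against a matched denominator the numerator cancels, so clustering leaves the factor unchanged. It would matter only if the target were the on-drug rate.

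A reader might also infer that early discontinuers drive the error. The ratio 28 days to treatment time is largest for them, but the rate pools all time, and they are the subjects most likely to have less than 28 days observed.

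**Conclusion.** The mismatch is certain from the text, and its direction is fixed: every non-zero crude TEAE rate exceeds the rate on a denominator matched to the TEAE window, by one common factor.

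The size rests on an assumed mean exposure. One might take the 1-year figure of 7.7% as typical, but the documents point to longer treatment. All 15 subjects rolled over from studies 040 and 041, and none had received placebo (SAP 3). The 52-week limit applies to subjects enrolled under Amendment 2 (Protocol synopsis, Study Periods). Protocol 1.6.2 already describes roll-over subjects with up to 2 years of data, and the visit-window footnote in SAP 13.1 runs to Week 253. If mean exposure was about three years or more, the overstatement is about 1 to 3% at most; at two years it is up to 3.8%. Early dropout could shorten the mean, so a larger figure cannot be excluded.

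This is a small definitional bias in absolute rates. It is worth correcting because the correction is nearly free, not because it would change a conclusion about safety.

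**What to change.** For TEAE rates only, define each subject's time at risk as

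(min(last dose + 28 days, death, last contact) - first dose + 1)/365.25,

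sum it over subjects, and use that sum in SAP 11.1. Keep PEY as defined in SAP 8.1 for exposure.

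The alternative is to keep PEY as the denominator and count only events on or before last dose. That estimates the on-drug rate and changes only terms that have a post-dose event. Either is coherent, but they answer different questions, so the SAP should state which is used. If the tables are to stay as they are, a footnote should give the two windows.

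The cost is one derived variable and one footnote, from dates already collected. With the matched denominator, the reported rates become slightly lower.

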11.2 CLINICAL LABORATORY PARAMETERS

Descriptive statistics for the following laboratory values and changes from baseline at selected time points are presented to include (but not limited) to the following:

Hematology: Hemoglobin, hematocrit, RBC count, CHr, MCV, WBC count, WBC differential, and platelet counts;

Chemistry: Alkaline phosphatase, ALT, AST, total bilirubin, TSAT, ferritin, total cholesterol, LDL cholesterol, HDL cholesterol, LDL/HDL ratio, CPK, LDH, total protein, albumin, fasting glucose, phosphate, uric acid, BUN, creatinine, sodium, and potassium; HbA1C;

11.3 VITAL SIGNS

Blood Pressures and Heart Rate baselines are defined as the mean of values obtained from the last 2 weeks of screening including Day 1 prior to the first dose.

Descriptive statistics are provided for vital signs (e.g., systolic and diastolic blood pressure, MAP, pulse rate, and respiratory rate) and their changes from baseline at each visit and at the end of study.

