1.3. Treatment of Anemia

Today, therapy with an erythropoiesis-stimulating agent (ESA) is a major alternative to transfusion in managing anemia associated with CKD. For those not resistant to ESAs, parenteral administration of exogenous recombinant human erythropoietin (epoetin alfa or beta) or pegylated analogues has been a widely accepted approach for treatment of anemia in patients with CKD (Eschbach, 1987; Eschbach, 1989; Winearls, 1986), despite the documented safety risks. These safety risks include hypertension and thrombosis, and may be associated with the supraphysiologic plasma EPO levels frequently observed with ESA therapy. Anemic patients with CKD or ESRD will require life-long treatment with these agents.

There is currently an unmet medical need for a convenient oral treatment that will correct anemia in CKD non-dialysis and dialysis patients to a target Hb level that is safe and well tolerated. An ESA dose relationship to mortality has been reported: higher mortality rates in ESRD patients targeting a higher Hb were reported in the Normal Hematocrit Study (Besarab, 1998) and a review of the USRD database (Zhang, 2004). Therefore, a treatment option that avoids supraphysiologic levels of circulating plasma EPO levels may be a safer alternative. Furthermore, ESA therapy for anemia in ESRD patients on HD usually requires concomitant intravenous (IV) iron supplementation therapy. Roxadustat is an oral medication that will potentially deliver effective treatment for CKD related anemia with less need for iron supplementation and without producing supraphysiologic levels of circulating EPO.

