1.6.3. Safety

The overall frequency and type of treatment-emergent adverse events (TEAEs) and serious adverse events (SAEs) observed in these clinical studies reflect events that would be expected to occur in CKD subjects with multiple co-morbidities and on a number of concomitant medications. There has been no SAE attributable by the sponsor to the use of roxadustat. Safety analyses did not reveal any association between the rates of occurrence of cardiovascular events with roxadustat, or any effect on AE rates related to either increasing Hb levels or on the rate of change of Hb levels.

Adverse event rates of hypertension (1% in Study FGCL-SM4592-017, 7.6% in Study FGCL-4592-041, and 10% FGCL-4592-053) and serious adverse events of arteriovenous-fistula thrombosis (overall incidence in dialysis-dependent CKD subjects: 2%), compare favorably with the rates reported in published ESA studies in similar subject populations (Krapf and Hulter 470-80; Fishbane and Besarab 1274-82). No safety risks were associated with increased rate of rise of Hb levels or with achieving a Hb level above 11 g/dL using roxadustat. Although Study FGCL-4592-041 subjects achieved Hb > 11 g/dL in 52% of exposure time during study, no cardiovascular safety events (death, MI, stroke, unstable angina, hospitalization for congestive heart failure, or hospitalization for arrhythmias) were reported while Hb > 11 g/dL during treatment with roxadustat.

No increased cancer risk has been noted with roxadustat treatment; however, the study program was not powered to detect absence of cancer risk.

Liver enzymes were monitored closely throughout the roxadustat clinical development program. Increases in liver enzymes were infrequently seen, and were generally mild and transient in nature. No cases of Hy's Law were observed throughout the program. An independent data and safety monitoring committee concluded that there was no concern for hepatotoxicity with roxadustat.

Based on the safety data collected to date, roxadustat has an acceptable safety profile that supports its further development.

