3 STUDY DESIGN

This is an open-label, long-term maintenance study of roxadustat anemia therapy in dialysis and non-dialysis subjects with CKD who completed the treatment period of a Phase 2 roxadustat anemia study in the U.S.

Subjects who received roxadustat in a previous study continued to receive roxadustat at the same dose and frequency as they received at the end of the treatment period in their previous study, unless a dose adjustment was required, at time of switching over to this study. Roxadustat was supplied in an open-label manner to all subjects.

This study (amendment 2) accommodated the potential for prior study participants on a placebo, to switch to this study: Subjects who received placebo in their previous study could start treatment with roxadustat at starting doses according to their weight (Appendix B of the protocol). Planned total study duration was up to 312 weeks (6 years), including up to an additional 1 year under Amendment 2.

Study visits were scheduled every 2 weeks, for the first 104 weeks (2 years) of study drug treatment (time on the previous Phase 2 studies of roxadustat), followed by every 4 weeks until the end of the treatment period.

After the end of treatment (defined as the last day a subject receives study drug) the subjects returned for a follow-up visit 4 weeks later.

The baseline Hb value for efficacy analysis is defined as the mean of the central laboratory Hb value from the baseline visit at Day 1 (prior to receiving the first dose of study drug in this study), plus any other central lab Hb values within 15 days prior to Day 1.

Safety is assessed by vital signs, physical examinations, clinical laboratory values (serum chemistries including liver function tests [LFTs] and complete blood counts [CBC]), electrocardiograms (ECGs), AEs and concomitant medication reporting. Clinical laboratory tests, including LFTs and Hb levels, could y be assessed at additional times on unscheduled visits for safety reasons.

Fifteen subjects entered this study: 1 subject from FGCL-4592-040 and 14 subjects from FGCL-4592-041. All subjects received Roxadustat prior to entering this study (0 subject received placebo). Descriptive analyses will be performed for all subjects.

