5 GENERAL STATISTICAL CONSIDERATIONS

5.1 SAMPLE SIZE DETERMINATION

This is an open-label, long-term maintenance study of roxadustat anemia therapy in dialysis and non-dialysis CKD subjects who have completed the treatment period of a phase 2 roxadustat anemia study in the U.S. The study allowed up to 50 non-dialysis, HD, and PD subjects, from up to 20 study centers throughout the U.S.

No power analysis was used to determine the sample size. Analysis Populations

All subjects entered into this study are included for the statistical analyses.

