9 CONCOMITANT MEDICATIONS

The World Health Organization Drug Dictionary (WHODD) Version 15 is used to classify concomitant medications by therapeutic class and preferred term based on ATC code level 3. Concomitant medication is defined as any medication taken between the day of first dose of the study medication and the day of last study medication date. For this study, all medication reported are considered as concomitant medication.

Concomitant medication usage is summarized by the number and proportion of subjects receiving each medication within each therapeutic class using the safety population. Multiple drug usage by a patient is counted only once.

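### A blood-pressure rise controlled by an added antihypertensive reaches no summary table in the SAP unless it is also recorded as a new or higher-grade adverse event

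*SAP*

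**What the plan says.** - **BP summary.** SAP 11.3: "Descriptive statistics are provided for vital signs (e.g., systolic and diastolic blood pressure, MAP, pulse rate, and respiratory rate) and their changes from baseline". SAP 5.2 defines descriptive statistics for continuous variables as n, mean, SD, median, quartiles, minimum and maximum. No threshold, shift or outlier category is given for BP.
- **Which reading counts.** SAP 5.3 uses derived analysis visits in all analyses and keeps the last of several measurements; the maximum is kept only for CPK, WBC and liver tests. SAP 13.2 also takes the last assessment in a window. It says all post-baseline assessments feed the determination of potentially clinically significant values, but the SAP gives no such criterion for BP.
- **Medications.** SAP 9: "For this study, all medication reported are considered as concomitant medication", and "Multiple drug usage by a patient is counted only once". Nothing separates drugs ongoing at entry from drugs started later.
- **Adverse events.** SAP 11.1 tabulates treatment-emergent events by preferred term, maximum severity and relationship, and as events per 100 patient-exposure-years. A condition present before the first dose counts only if its severity increased.
- **Why BP matters here.** Protocol 1.3, on ESAs: "These safety risks include hypertension and thrombosis, and may be associated with the supraphysiologic plasma EPO levels frequently observed with ESA therapy". Protocol 1.6.3 gives figures for roxadustat: "Adverse event rates of hypertension (1% in Study FGCL-SM4592-017, 7.6% in Study FGCL-4592-041, and 10% FGCL-4592-053". Protocol 1.6.2 adds that rapid Hb rises on roxadustat came without the BP elevations reported for ESAs.

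**The concern.** Long-term safety is part of the primary objective, and the protocol already makes a favourable statement about blood pressure. Treatment was planned for up to 6 years in open-label care. If BP rises and the physician adds a drug, later readings reflect the drug as well as the underlying pressure. The BP summary then leans towards showing no change, and the medication table, which would ordinarily reveal the added treatment, is built so that it cannot. At stake is false reassurance on a harm that the sponsor itself follows.

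**Working it through.** There is no planned figure to reproduce: "No power analysis was used to determine the sample size". The check traces a treated rise through the tables, then gives sizes.

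**1. Inputs from the documents.** "Fifteen subjects entered this study: 1 subject from FGCL-4592-040 and 14 subjects from FGCL-4592-041", so n = 15. "All subjects received Roxadustat prior to entering this study (0 subject received placebo", so baseline is on drug. Earlier hypertension event rates: 1%, 7.6% and 10% (Protocol 1.6.3).

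**2. Where a treated rise could appear.**

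| Summary | Rise treated, event recorded as new or higher grade | Rise treated, no such record |
|---|---|---|
| BP values and changes (SAP 11.3) | Pulled back towards baseline | Pulled back towards baseline |
| Medications (SAP 9) | Looks the same as a drug taken since before entry | Looks the same as a drug taken since before entry |
| TEAE tables (SAP 11.1) | Counted | Not counted |

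**3. Can the high reading itself drop out?** SAP 13.1 places BP at Weeks 4, 8, 12 and then every 12 weeks, with target day 7 × week + 1 and a window of half the distance to the next target.
- Week 24 target: 7 × 24 + 1 = Day 169. Week 36 target: 7 × 36 + 1 = Day 253. Half the gap: 84 / 2 = 42 days.
- The Week 24 window therefore runs from about Day 127 to Day 211. It contains Week 20 (Day 141) and Week 28 (Day 197).
- Under the last-value rule, a high Week 20 reading treated by Week 28 does not enter the summary. The reported maximum is then a maximum of last values.
- SAP 11.3 speaks of each visit, but SAP 5.3 makes the analysis visits govern all tables.

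**4. Does the adverse event route work?** Expected subjects = 15p; chance of at least one = 1 − (1 − p)^15.
- p = 1%: 0.15 subjects; 14%
- p = 7.6%: 1.14 subjects; 69%
- p = 10%: 1.5 subjects; 79%

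The rates come from studies of different length, so they show only that this route is a real one. Fourteen of the 15 subjects came from the study with the 7.6% rate, and hypertension that arose there is pre-existing here.

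**5. Illustration of masking (all values assumed).** If k of 15 subjects rise by r mmHg and a fraction f is removed by added drugs, mean change = k·r·(1 − f)/15.
- k = 4, r = 20: 80/15 = +5.3 at f = 0; +2.7 at f = 0.5; 0.0 at f = 1.
- Over k = 2 to 6 and r = 10 to 20: +1.3 to +8.0 untreated; 0.0 fully offset.
- If each of the 4 had a drug added, a count of new antihypertensives shows 4/15 = 26.7% (exact 95% CI 7.8% to 55.1%) whatever f is.
- Half-width of the 95% CI for the mean change, 2.145 × SD/√15: 8.3 mmHg at SD 15 and 11.1 mmHg at SD 20. The SDs are assumed; the documents give none.

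**The case against.** A reader might infer that hypertension is analysed only as mean BP change and that a treated rise vanishes from the report. The documents do not support that. SAP 11.1 counts hypertension by preferred term, severity and rate, including worsened pre-existing disease. This is the form in which the protocol quotes its own figures. SAP 5.2 reports quartiles and extremes, so an untreated rise in 4 of 15 subjects would show in the maximum even when the mean is within noise. Nor does the protocol call hypertension the main ESA risk; it lists it with thrombosis.

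Other points also stand. Sites query for adverse events at every visit (Protocol 11.3.1) and must give an indication for each drug (Protocol 4.4.1). All assessments are listed, and 15 subjects can be read one by one. Table specifications sit in a separate document that might hold a BP criterion. SAP 11.3 follows Protocol 10.6.4, which planned BP as values and changes. No passage shows that unrecorded escalation is common.

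This narrows the gap without closing it. Protocol 11.3.6 says that laboratory changes needing active management may be adverse events; no parallel rule covers vital signs. Whether adding a drug raises the grade depends on a scale that is cited but not reproduced. Protocol 10.6.4 also planned concomitant medications by time point, as appropriate; SAP 9 carries no time dimension.

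**Conclusion.** The point holds in a limited form. The SAP has no BP category and no count of newly started antihypertensives. Adverse event recording is therefore the only route by which a treated rise reaches a summary table, and the BP summaries cannot be interpreted apart from treatment. It would go too far to say that the plan will produce a false finding of no change. That needs drugs to be added without a new or higher-grade event, and the documents do not say how often this happens.

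The size is illustrative: in the assumed case, the mean change falls from +5.3 to 0.0 mmHg while 4 of 15 subjects have been given more treatment. At n = 15 the mean is imprecise even without masking. The study has one arm and every subject was on roxadustat at entry, so what is lost is descriptive information, not a test result.

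**What to change.** - **SAP 9:** split medications into those ongoing at Day 1 and those started after Day 1, using start dates (imputed under SAP 13.7 where partial) and the recorded indication. First repair the missing-day rule for start dates in SAP 13.7: its two branches state the same condition. Note also that a start date with only the entry year known is set to the first dose date, so it would not count as new; report how many dates were imputed.
- **SAP 11.3, table 1:** number (%) of subjects, and events per 100 patient-exposure-years, with a newly started antihypertensive after Day 1. Add dose increases only if doses of concomitant drugs are recorded; no passage shows that they are.
- **SAP 11.3, table 2:** number (%) of subjects with post-baseline BP in a pre-specified high category not met at baseline, based on all post-baseline readings and taken from NCI CTCAE v4.0, which Protocol 11.3.2 already cites.
- **Interpretation:** state that BP change is to be read with these counts.

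The cost is two tables, one derived flag and a coding review for 15 subjects. No new data collection is needed for the new-start count. The counts remain descriptive and cannot separate drug effect from progression of kidney disease.
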